# HRA PROTOCOL COMPLIANCE DECLARATION

This protocol has regard for the HRA guidance and order of content

### RESEARCH REFERENCE NUMBERS

IRAS: 336518

Funder Number: NIHR Doctoral Research Fellowship Round 9. Award Reference: NIHR303289.

Sponsor Reference Number: 2024-NCT03

# STUDY SUMMARY

Study Title	Study of PhOTobiomodulation impLementatIon for mucosiTis managEment in children	
Internal ref. no. (or short title)	SPOT-LITE	
Study Design	Mixed methods	
	Work-package 1: Qualitative semi-structured interviews will be undertaken with diverse stakeholders in photobiomodulation implementation.	
	Work-package 2: Co-creation of an implementation package with a diverse group of stakeholders.	
	Work-package 3: Mixed-methods evaluation of implementation package at three children's cancer centres. Data collection consisting of lightning reports, quantitative patient-reported outcome measures and qualitative focus groups.	
Study Participants	Work-package 1: Qualitative semi-structured interviews with an anticipated 20 healthcare professionals, commissioners and equipment manufacturers and 5 dyads of children and young people (CYP) and their parents.	
	Work-package 2: A co-design group will be formed, consisting of cancer care commissioners, healthcare professionals (HCPs - dentists, dental nurses and therapists, doctors, nurses), patients and parents, equipment manufacturer representatives, and healthcare	

	researchers. Up to 20 stakeholders will be involved, including at least five parents and CYP, and at least one member of each named professional group across different geographical locations.  Work-package 3: Three children's cancer centres will be purposively sampled to ensure: different photobiomodulation implementation stages in relation to the Rogers Adoption Curve (early majority, late majority, laggards), different geographical areas, different number of eligible cases, different cancer treatments, and, presence or absence of specialist Paediatric Dental teams. Lead clinicians will be recruited from these sites who will take part in lightning reports and will oversee collection of treatment and anonymised patient data for outcome evaluation as part of a locally registered service evaluation. Up to eight healthcare professionals, purposively sampled by professional role, will be recruited at each children's cancer centre to take part in a focus group at six months.
Planned Size of Sample (if applicable)	Work-package 1: 20 healthcare professionals and 5 CYP & Parent Dyads (n=10). 30 participants.  Work-package 3: Three children's cancer centres sampled by site; one lead clinician and up to seven further healthcare professionals to be recruited at each site for focus groups. 24 participants.
Follow up duration (if applicable)	Not applicable for work-packages 1 & 2.  For work-package 3, focus groups planned at six months following implementation to evaluate sustainment of knowledge and services.
Planned Study Period	30 months from ethical and HRA approvals, up to September 2026
Research Question/Aim(s)	RESEARCH QUESTION: Does a theory and evidence-based approach to implementation increase the uptake of photobiomodulation in U.K. children's cancer centres?  AIM: To identify determinants of implementation of photobiomodulation services for children to increase uptake, sustainability, and mucositis management

# FUNDING AND SUPPORT IN KIND

FUNDER(S)	FINANCIAL AND NON-FINANCIAL
	SUPPORT GIVEN
National Institute of Health and Care	Funding in Round 9 of Doctoral Research
Research	Fellowships – awarded to Chief Investigator as a personal award [name]. Funding commenced October 2023 to cover: project costs, salary and training plan
	of Chief Investigator.
	Award reference: NIHR303298, value
	£457,522
Candlelighters Children's Cancer	Charity Number: 1045077
Charity	
	Non-financial support for patient and public
	involvement: facilities, advertisement
	through Candlelighters mailing lists,
	networks and social media.
	Non-financial support for recruitment of
	children and parents into research:
	advertisement through Candlelighters
	mailing lists, networks and social media.
	Equivalent to £2,100 matched funding

# **ROLE OF SPONSOR AND FUNDER**

The University of Leeds acts as the Sponsor for this study and assumes overall responsibility for the initiation and management of the study.

The National Institute of Health and Care Researcher acts as the funder of the study.

### 2) Patient and Public Involvement Group

- o [name], bereaved parent with lived experience of having a child with mucositis
- o Flexible approach to child and young person involvement planned (see below)

To ensure the voice of CYP with cancer is central to this project, PPI involvement is costed throughout the research to remunerate contributors for time and expenses, following INVOLVE guidance.

The research is supported by Candlelighters, a charity dedicated to supporting families of children diagnosed with cancer within Yorkshire. Their family support team, headed up by [name], will support PPI recruitment and activities, and dissemination (equivalent to a £2,100 in matched funding). [name] is a bereaved parent who contributed to our preliminary PPI. She has agreed to join my project advisory group, alongside [name] and a CYP representative, to provide input and lived experience.

A child and their family's life can be subject to significant change, particularly during cancer treatment. Insights from other research projects led by my supervisor [name] have highlighted a need for a responsive model of research involvement, sensitive to the life stage of CYP. Therefore, engagement is planned throughout, with different representatives likely to contribute at different time points and to different activities. Our PPI representatives have highlighted the importance of flexibility to reduce time burden, including use of email and video conferencing as alternatives to face-to-face meetings. Research involving CYP with cancer relies on the ability to contact families and Candlelighters' support has proven invaluable in engaging these families.

Following an initial training event to support representatives in their contribution, biannual meetings with eight PPI representatives are scheduled throughout the research project. Initial PPI consultation has occurred to support finalisation of the study protocol, topic guides and documents. Infographics will be created following PPI meetings to demonstrate impact on research design, these will be disseminated as the fellowship progresses. In addition to biannual meetings, consultation will occur with smaller PPI subgroups for: website content design, qualitative research training and analysis, video co-creation and dissemination event planning.

# 3) Protocol Contributors

[figure not shown]
This protocol has been developed by the Chief Investigator ([name]), with support from the PhD Supervisory Team ([name], [name], [name]) and qualitative researchers (AC, [name]). Training and support in delivery of co-creation activities has been provided by [name], co-designer and project manager at NIHR Children and Young People MedTech Cooperative.

The protocol has received external peer review, through the process of applying for competitive Doctoral Research Fellowship funding through the National Institute of Health and Care Research.

The protocol, ethics application and accompanying documents have been reviewed by the Project Advisory Group. Project outline was reviewed by PPI contributors prior to the funding application, and again prior to ethics consideration. Protocol and study documents have also undergone Sponsor review prior to submission for ethical approval.

**KEY WORDS:** Mucositis, Paediatric Oncology, Implementation, Photobiomodulation, Co-creation

#### SCHEMATIC OVERVIEW OF STUDY

# 1. BACKGROUND

### THE DISEASE

An estimated 450,000 childhood cancer diagnoses occur globally each year, with the U.K. recording 1,838 new diagnoses in 2018. Childhood cancer has a high cure rate, with a five-year survival of 84% in 2012-2016. Childhood cancers respond well to chemotherapy, and most children and young people (CYP) receive chemotherapy during their cancer treatment. In the U.K., these intensive treatments are delivered in 20 principal treatment centres, with some lower intensity treatments delivered in shared-care district general hospitals or Paediatric Oncology Shared Care Units (POSCUs).

Oral mucositis affects up to 8 out of 10 CYP receiving chemotherapy, usually within 3-10 days of initiating treatment and can persist for up to 3 weeks. Mucositis has a significant biopsychosocial

impact on CYP. In severe cases, CYP require hospitalisation for parental nutrition and pain-relief, delaying scheduled chemotherapy. CYP who experience treatment delays and de-intensification of chemotherapy are at increased risk of treatment failure. Preventing mucositis matters to patients, carers *and* oncology services; mucositis reduction minimises treatment disruption, reduces individual and societal costs and reduces burden of care.

### **PREVENTION**

A practical treatment that can prevent and reduce severity of mucositis is photobiomodulation (PBM), the application of red LED light or low-level laser to oral tissues during chemotherapy.  Our previous research identified that photobiomodulation is only available in 2 of 20 U.K. children's principal treatment centres.  The Pediatric Oncology Group of Ontario (POGO), a leading inter-professional group producing clinical practice guidance for Supportive Cancer Care for CYP, recommend the use of photobiomodulation for children at high risk of developing mucositis. 

### THE PROBLEM

Photobiomodulation is a complex, multidisciplinary intervention, with several requisite interprofessional behaviours and skills that must interact in different contexts and settings for successful implementation. The latest MRC-NIHR framework for developing and evaluating complex interventions has a scope that goes beyond "effectiveness" to consider implementability, cost-effectiveness, transferability, and scalability in real world conditions. Using this effectively could help increase the uptake and reduce unwarranted variability in PBM implementation in principal treatment centres and children's cancer care more widely.

Implementation research promotes the uptake of evidence-based practice into routine care and explores the influences on healthcare professional and organisational behaviour.  Research relating to implementation of complex interventions, such as photobiomodulation, in different contexts can provide the basis for generalisable resources to implement interventions in clinical service contexts. 

# 2. RATIONALE

### **HEALTHCARE NEED**

CYP with cancer rank interventions addressing treatment side-effects as their second most important research priority in a James Lind Alliance priority setting exercise. Managing side-effects is a key component of supportive cancer care delivered by multi-disciplinary teams.

We have engaged CYP and their families in our patient and public involvement (PPI) groups using a "public science fair" stall and individual engagement sessions. Our PPI groups identified prevention of oral mucositis as highly important to CYP and their families. Families tell us oral mucositis can often be "the worst thing" about their child's cancer treatment, accompanied by feelings of "helplessness" when seeing their child unable to eat or drink.

Oral mucositis is most often managed with oral care advice, including oral hygiene instruction and maintaining hydration. Mouthwashes such as chlorhexidine or benzydamine for pain relief and topical barrier gels are also used. These treatments aim to relieve symptoms, rather than prevent mucositis. Our PPI representatives found mouthwashes were often "frustrating" and "impossible" to use when their mouths were painful. CYP and their parents tell us they want a viable treatment for preventing oral mucositis from happening during cancer treatment.

Photobiomodulation can prevent mucositis, or reduce its severity when it does occur. Research shows that it is cost-effective in adults when compared to standard oral care, with an incremental cost-effectiveness ratio of \$2868 and \$4961 reported in two studies,  due to reduction in costs related to pain-relief, nutrition and hospitalisation. However, there is a paucity of economic evaluation in CYP.

### **RESEARCH GAP**

This fellowship would fund empirical research and theoretical development exploring how best to implement photobiomodulation into U.K. children's cancer care and to co-create and test an implementation package. This would support implementation of photobiomodulation services and improve availability of this preventative treatment for CYP, reducing their risk of developing severe mucositis and the associated impact on cancer care and quality-of-life.

The implementation package would be transferrable and adaptable, able to support implementation of other evidence-based supportive cancer treatments in the future. Wider implementation of this complex intervention, supported by the fellowship results, would enable recruitment into clinical photobiomodulation trials.

This proposed research aims to test implementation theories in the novel context of children's supportive cancer care, to explore their value in developing other implementation interventions in this context. This aligns with the NIHR's focus on implementation science and knowledge mobilisation in their funding of advanced fellowships in the current recruitment round.

This doctoral fellowship will enable my post-doctoral plans for conducting a hybrid randomised trial exploring both clinical and cost effectiveness and implementation. Such a trial would aim to reduce uncertainty around degree of effectiveness of photobiomodulation in CYP and establish treatment parameters and regimes, whilst determining cost-effectiveness and evaluating implementation strategies in different contexts.

#### REVIEW OF EXISTING EVIDENCE

Photobiomodulation is an intervention with real potential clinical utility based on a growing evidence-base and subsequent recommendations for its use. An initial Cochrane review in 2011 found weak-evidence to support photobiomodulation use during chemotherapy. In 2018, following literature review, NICE recommend photobiomodulation during chemotherapy or radiotherapy. Similarly, the Mucositis Study Group of MASSC/International Society of Oral Oncology recommend photobiomodulation for patients undergoing haematopoietic stem cell transplant (HSCT) or receiving head and neck radiotherapy.

In CYP, there are two notable systematic reviews with meta-analyses, one published in 2021 by a team led by my supervisor [name]. Meta-analyses showed an odds ratio of developing severe mucositis of 0.3-0.7 in the photobiomodulation groups compared to controls, depending on the time point analysed. These estimates remain uncertain, through heterogeneity of trial design and varied implementation.

The POGO Mucositis Prevention Guideline Development Group recommend photobiomodulation for cooperative children receiving chemotherapy or HSCT. This guidance was updated in 2021 to a strong recommendation, supported by high quality evidence in CYP. Research gaps highlighted including the feasibility of treatment in CYP and uncertainty around economic evaluation, and ideal treatment

parameters such as wavelength, timing, duration. My previous research, described below, has shown that availability, unwarranted variations, feasibility, and acceptability of this evidence-based, recommended treatment for CYP can all be improved.

### **ALTERNATIVE TREATMENTS**

There are few alternative treatments for mucositis prevention; cryotherapy (holding ice in the mouth throughout chemotherapy infusions) and keratinocyte growth factor (KGF) have the strongest evidence. Studies supporting cryotherapy are in adult populations involving shorter duration chemotherapy regimens not commonly used in CYP, and a recent feasibility study found low compliance with cryotherapy among CYP. Our PPI representatives felt this would have been "impossible" during chemotherapy infusions over several hours. Similarly, KGF is expensive, has an unknown toxicity profile, and there is a paucity of paediatric research in this area. POGO therefore discourage routine KGF use in CYP.

### TIME AND RELEVANCE

Engagement from our PPI groups, and the CCLG with our survey, show this topic is of interest to CYP and children's cancer services. The proposed fellowship would use implementation theory to evaluate how best to address the implementation gap. Wider national and international implementation of photobiomodulation services will enable high-quality clinical trials of sufficient statistical power, to fine-tune treatment parameters and modalities and to improve certainty around effect size and economic evaluation in CYP, as highlighted as research gaps in the POGO guidance. Additionally, wider availability of this preventative treatment for CYP undergoing cancer treatment will improve their quality-of-life and treatment outcomes.

### 3. THEORETICAL FRAMEWORKS

### **UNDERPINNING THEORIES**

In implementation research, frameworks contain the theoretical constructs required for systematic application and the theoretical "lens" through which to study implementation. Frameworks offer an evidence-based foundation for implementation research, promoting methodological rigour and transferability. Frameworks have differing purposes and uses. Three frameworks are used in my planned research; each justified by their (project) function and the implementation question being addressed. Photobiomodulation provides a test-bed for evaluating and refining these frameworks and exploring their descriptive and predictive value in the novel context of supportive cancer care for children.

#### Knowledge to Action Framework (KTA)

The KTA is an iterative and dynamic process of knowledge creation and application for improving healthcare. It is a social constructivist model, placing importance on social interaction and adaptation of research evidence into local context. Social and local environmental influences were identified as contextual barriers to implementation in our previous survey research. KTA offers an appropriate collaborative framework for this project, which aims to bring knowledge producers and users together to hasten and broaden adoption of PBM. It has a strong track record as a basis for developing multi-component interventions to support implementation - with 146 studies using the KTA in a 2014 systematic review. In my fellowship, KTA provides the scaffolding surrounding the overarching project plan.

It provides a strategy for implementing photobiomodulation through seven phases outlined in the schematic diagram, with key phases outlined throughout the methods in *italics*.

Consolidated Framework for Intervention Research (CFIR)

The CFIR provides a framework for developing specific interventions to support implementation. The CFIR is a comprehensive framework, derived from 20 research sources from 13 different scientific disciplines. The CFIR contains 39 constructs within five domains: intervention characteristics, outer setting, inner setting, characteristics of individuals, process of implementation. The CFIR provides the framework to approach implementation research pre, peri and post-implementation. It can be used to explore the conditions in which implementation has succeeded or failed, and identify modifiable factors to support implementation. The CFIR will be used in work-package 1 to explore previous implementation experiences, to explore *why* implementation succeeds or fails.

### RE-AIM Framework

The RE-AIM framework is used to evaluate implementation outcomes (*who,what,where,when*). It provides a practical, systematic approach to evaluating implementation interventions and has been utilised in a wide variety of clinical, community and corporate settings. The RE-AIM framework considers five key domains of Reach, Effectiveness, Adoption, Implementation and Maintenance. It provides a more practical approach for planning and evaluating practice change interventions when compared to the CIFR. RE-AIM will be used for implementation evaluation in work-package 3.

### PREVIOUS WORK

My previous survey research on provision of photobiomodulation to CYP in the UK through the CCLG has *evaluated the knowledge to action gap*.  I have led the formation of a national collaborative of Paediatric Oncologist and Paediatric Dentists in this area. These existing relationships support purposive sampling and recruitment for our planned research.

### 4. RESEARCH QUESTION, AIM AND OBJECTIVES

**RESEARCH QUESTION**: Does a theory and evidence-based approach to implementation increase the uptake of photobiomodulation in U.K. children's cancer centres?

**AIM**: To identify determinants of implementation of photobiomodulation services for children and young people to increase uptake, sustainability, and mucositis management

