#### **Work-package 3: Testing of implementation package**

The implementation package will be evaluated at three children's cancer centres at different stages of implementation through a mixed-methods approach. In the context of this study the implementation package in itself is the intervention, not the photobiomodulation treatment, which is an evidence-based treatment recommended in multiple clinical practice guidelines.

Study design: Mixed-methods consisting of lightning reports, quantitative patient-reported outcome measures and qualitative focus groups. Quantitative data allows exploration of *use of knowledge* and *outcome evaluation*. Qualitative focus groups and biweekly lightning reports provide experiential data regarding use of the implementation package, and perceived *use of knowledge*. However, they are subject to hindsight, social desirability bias and group think. A mixed-methods approach following the triangulation convergence model is therefore planned, where qualitative findings will be compared to quantitative findings to aid interpretation and improve validity.

Ethical approval and consent: Ethical approval will be sought from the NHS REC, with support from the University of Leeds as sponsor, and research offices at each site confirming capability and capacity. Additional participant sites will be added as amendments as required.

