### ii) Quantitative data

A lead clinician within each children's cancer centre will oversee collection of treatment and patient data for *outcome evaluation* as part of a locally registered service evaluation. Anonymous clinical variables to be collected include: proportion of CYP eligible for treatment who have received PBM and

data collected as part of photobiomodulation treatment – treatment refusals, clinician reported World Health Organisation Mucositis grading and patient reported Children's International Mucositis Evaluation Scale (ChIMES).. This enables *outcome evaluation* from a patient and provider construct and provides feasibility data on completion of these outcome measures as part of standard NHS care. This anonymous data will be analysed at the level of the centre.

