# Work-package 3: Testing of the implementation package

Three children's cancer will be purposively sampled to ensure: different photobiomodulation implementation stages in relation to the Rogers Adoption Curve (early majority, late majority, laggards), different geographical areas, different number of eligible cases and, presence or absence of specialist Paediatric Dental teams (as this has been reported as an implementation facilitator in our previous research). Additionally, sampling will aim for diversity in the children's cancer setting, and may include Principal Treatment Centres, Paediatric Oncology Shared Care Units (POSCUs) and other cancer treatment settings such as specialist radiation or stem cell services. This will allow testing of the

implementation package in different contexts to evaluate external validity and transferability through the Knowledge to Action lens. A sample of three sites has been chosen to allow sufficient variation in outer and inner settings in KTA, within the confines of the number of eligible pre-implementation treatment centres.

Potential participant sites are likely to change over time, with continued adoption of photobiomodulation. At the time of application, Alder Hey Children's Hospital (where specialist paediatric dentistry services are present) are at the point of pre-implementation, with interest in adoption expressed through our national network. Southampton Children's Hospital (where specialist paediatric dentistry services are absent) are at the stage of beginning implementation and have requested resources and support through our national photobiomodulation network. Additionally, Great Ormond Street and The Christie Proton Beam Centre have been approached to take part. The CCLG is a network inclusive of all U.K. principal treatment centres and, alongside our national photobiomodulation network, supports recruitment.

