### **Work-package 3: Testing of the implementation package**

The Children's Cancer and Leukaemia Group is a network inclusive of all U.K. principal treatment centres. Additionally, the research team has an existing established national working group of lead clinicians with an interest in photobiomodulation, including clinicians at POSCUs and other cancer treatment sites. These networks will be utilised to support recruitment, with study information shared through these groups. Existing professional relationships and contacts as well as snowball sampling will also be utilised. Where snowball sampling is utilised, existing participants will email potential participants and copy in the research team.

Potential participant sites are likely to change over time, with continued adoption of photobiomodulation. Sites will be added to the ethics application as amendments at the time of recruitment.

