# Work-package 3: Quantitative outcome data

In work-package 3, anonymous clinical variables will be collected from patient records of all children receiving photobiomodulation during the 3 month implementation period at each individual cancer centre. This will include: proportion of CYP eligible for treatment who have received PBM and data collected as part of photobiomodulation treatment – age, cancer diagnosis, chemotherapy agent, treatment refusals, clinician reported World Health Organisation Mucositis grading, and patient reported Children's International Mucositis Evaluation Scale (ChIMES). Access to patient identifiable information will only be by members of the direct healthcare team in the relevant cancer centre.

This enables outcome evaluation from a patient and provider construct and provides feasibility data on completion of these outcome measures as part of standard NHS care. This anonymous data will be analysed at the level of the children's cancer centre by lead clinicians recruited to this research. The children receiving photobiomodulation are doing so as part of their standard NHS care, they are not research participants in themselves. Our patient and public contributors felt that collection of this non-identifiable data by members of the direct healthcare team for the purpose of this locally registered service evaluation was acceptable.

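### The research question asks whether photobiomodulation uptake increases, but work-package 3 measures uptake only after the package arrives, with no baseline or comparator

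*Protocol*

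**What the plan says.** The study summary and section 4 pose the same research question: "Does a theory and evidence-based approach to implementation increase the uptake of photobiomodulation" in U.K. children's cancer centres. Section 5 (work-package 3) makes clear what is being tested: "the implementation package in itself is the intervention, not the photobiomodulation treatment".

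The quantitative uptake measure, in section 5 (work-package 3, ii), is the "proportion of CYP eligible for treatment who have received PBM". Section 7.3.2 fixes the window: the clinical variables are "collected from patient records of all children receiving photobiomodulation during the 3 month implementation period" at each centre.

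Three centres take part and all receive the package. Section 7.1.1 selects them to be at different stages of adoption (early majority, late majority, laggards). It also refers to a limited pool of eligible pre-implementation centres. Of the candidates it names, one is at pre-implementation, while the staff of another "are at the stage of beginning implementation and have requested resources". Sections 7.1.1 and 7.3.1 both add: "Potential participant sites are likely to change over time, with continued adoption of photobiomodulation".

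The aim and objectives in section 4 are softer than the question: to identify determinants of implementation, to explore barriers and facilitators, to co-create the package, and to test and evaluate it.

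**The concern.** An increase is a difference between two values. The protocol collects one. To attribute an increase to the package, one also needs some account of what would have happened without it, and the design has no control centre, staggered start or repeated pre-package measurement.

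This is not a detail that can be left to an analysis plan. The protocol itself fixes the data window and the sites, and no later analysis can recover counts that were never extracted. What is at stake is whether the headline question gets a supported answer, and whether a report that uptake rose, or rose because of the package, could be defended.

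**Working it through.** **1. The protocol's own figure.** The only work-package 3 sample size is a headcount: 3 centres × (1 lead clinician + 7 further professionals) = 24. It reproduces. It concerns focus-group participants, not the uptake proportion. The protocol states no expected uptake, number of eligible CYP, alpha or power, so there is no power calculation to check.

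**2. When each data source is collected.**

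| Source | Timing | Can it serve as a baseline? |
|---|---|---|
| Uptake proportion (5, WP3 ii; 7.3.2) | 3-month implementation period | No |
| Lightning reports (5, WP3 i) | First three months of implementation | No; qualitative |
| Focus groups (5, WP3 iii; 6) | At, or up to, six months | No; qualitative |
| Earlier national survey (1, Prevention) | Before the study | No; see step 3 |

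The only comparison planned in work-package 3 is of qualitative with quantitative findings (triangulation). That compares kinds of data, not periods or groups.

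**3. Can the survey stand in?** It found PBM available in 2 of 20 principal treatment centres, 2/20 = 10%. That is availability counted by centre across the UK. The study measure is a proportion of patients within each of three chosen sites. The two cannot be subtracted, and no repeat survey is described.

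**4. What a single later value leaves open.** Change = later uptake − baseline uptake. All rates here are assumptions.

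| Later uptake | Baseline | Change (points) |
|---|---|---|
| 60% | 0% | +60 |
| 60% | 30% | +30 |
| 60% | 50% | +10 |
| 50% | 0% | +50 |
| 50% | 25% | +25 |
| 50% | 50% | 0 |
| 50% | 60% | −10 |

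For a fixed later value, the planned data fit every row in its block. Only where the baseline is known to be zero is the change determined.

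**5. What a baseline would and would not buy.** With three centres, the most favourable sign test (all three improve) gives p = 0.5³ = 0.125 one-sided and 2 × 0.125 = 0.25 two-sided. At patient level, ignoring clustering, with two-sided alpha 0.05, 80% power and an assumed later uptake of 50%, the eligible CYP needed per period would be 20, 58 or 388 for baselines of 10%, 25% or 40%. A before/after pair at three sites is therefore best presented as description.

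**The case against.** The strongest reply is that the baseline is close to zero by design. Section 7.1.1 speaks of pre-implementation centres. The work-package 3 list of adoption stages omits the early adopters that appear in the work-package 1 list. PBM was available in only 2 of 20 principal treatment centres. At a centre with no PBM beforehand, prior uptake is zero and a rise can be described. This stands. A reader might infer that no increase could ever be shown; the documents do not support that for such a centre. But zero is neither required for selection nor recorded, and stages are deliberately mixed. The site that was beginning implementation is only a candidate, and no uptake there is given, so it shows that zero cannot be assumed, not that the baseline was high.

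A reader might also take the protocol to say that adoption is rising without the package. It does not. The remark about continued adoption concerns which sites will be available. A background trend is a fair inference from it, not a stated fact.

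Third, one might conclude that the study fails altogether. That goes too far. The aim and objectives can be served by the planned data, no causal estimate or hypothesis test is planned, and section 2 leaves effectiveness and the evaluation of implementation strategies to a later randomised hybrid trial. What remains is that the stated research question asks for more than the design provides.

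**Conclusion.** The mismatch between question and data is real, in a limited form. At a site with truly no prior PBM, a rise from zero could be described but not attributed to the package. At any site already delivering PBM, even the size of the change cannot be determined: in the illustrations above, one later value is compatible with anything from +60 to +10 points, or from +50 to −10. Those rates are assumptions, and the true ambiguity depends on how much PBM the chosen sites were already giving, which the protocol does not state. The conclusion itself rests only on the collection window in section 7.3.2, the three centres all receiving the package, and the absence of any baseline or comparator.

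I would class this as should-fix. The remedy is inexpensive, no sample-size calculation depends on it, and the softer aim and objectives are unaffected.

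**What to change.** - In section 5 (work-package 3, ii) and section 7.3.2, have the direct care team also extract anonymous counts of eligible and treated CYP for the three months before the package is handed over at that centre. Where no PBM was delivered in that time, record that explicitly.
- Report numerators and denominators for both periods, by centre. State where the count of eligible CYP comes from: section 7.3.2 describes the records of children receiving PBM, whereas the proportion needs all who were eligible.
- Reword the research question (study summary and section 4), and the conclusion to be drawn, as a descriptive, uncontrolled before/after change in uptake at three centres, with no causal claim. If the earlier counts cannot be obtained at a site, limit the claim there to uptake during implementation.

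Cost: some extra retrospective extraction per site, harder where eligibility for PBM was not being recorded. Section 8.1 undertakes to keep the burden on lead clinicians low, so the request should stay at two counts. The local service-evaluation permissions in section 8.6 must cover the earlier period. The resulting claim is more modest, and it stays descriptive even with the added data.
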